4.2. Scientific Rationale for Study Design

A double-blind, placebo-controlled study was selected where guselkumab or placebo would be randomized in addition to standard-of-care background therapy. This study design was selected as a true placebo comparator group is unethical for this serious disease condition. Therefore, placebo and experimental treatments will be added to a standard-of-care regimen of MMF/MPA and glucocorticoids.

With this standard-of-care regimen, participants will enter on glucocorticoids (at minimum prednisone equivalent dose of 10 mg/day and not exceeding 1 mg/kg/day or 60 mg/day prednisone or its equivalent, whichever is lower) and will be tapered fairly rapidly to 5 mg/day prednisone equivalent by Week 12 to minimize confounding treatment effects of glucocorticoids on major efficacy endpoints, as has occurred in several, negative LN studies.¹⁴ Similar glucocorticoid tapers have been used in some recent LN studies.³¹

For participants who will be treated with guselkumab, an IV induction dose of guselkumab initially through Week 12 was chosen, followed by SC doses as this follows the typical induction-maintenance treatment paradigm for Class III/IV LN. This ensures target inhibition of IL-23 in the kidney in this proof-of-relevance study. This dose of guselkumab is also being evaluated in a Phase 2b/3 study in UC. Additional details are described in Section 4.3.

A primary analysis at Week 24 will be conducted for proof-of-concept and to allow for Phase 3 LN program planning.

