A summary of allowed glucocorticoid dosing at randomization and changes during the study are shown in [Table 5](#) and in [Table 6](#), respectively. A glucocorticoid tapering schedule starting from Week 2 down to 5 mg po qd prednisone equivalent by Week 12 is provided in Appendix 7 [Section 10.7]. It is required that all participants adhere to this steroid tapering schedule as closely as possible. Significant deviation from this tapering schedule should be discussed with the medical monitor. Glucocorticoid doses should not be changed to start within one of the columns of the tapering schedule. If a participant falls between the doses noted in 2 adjacent columns (eg, 55 mg instead of 50 or 60 mg), the investigator should make a clinical decision as to which column they should be tapered to (eg, 30 or 40 mg) then stay within that column for the rest of the taper. A participant's lowest glucocorticoid dose should be 5 mg po qd through Week 24 unless an AE requires discontinuation. Reason(s) for not tapering glucocorticoids should be documented.

Additional considerations of oral glucocorticoid use during the study are as follows:

- If a participant experiences worsening disease activity while tapering glucocorticoids from Weeks 2 to 12, further dose decreases may be suspended, and/or their oral glucocorticoid dose may be temporarily increased (ie, glucocorticoid rescue) if deemed necessary by the investigator.

- Increases in average daily glucocorticoid dose that exceed the baseline dose may trigger TF rules. If glucocorticoid tapering is interrupted, Investigators are encouraged to resume tapering as soon as it is practical.
- Increases above 10 mg/day prednisone equivalent after Week 12 will be considered a TF.
- It is recommended that participants be educated about and monitored for symptoms of steroid adrenal insufficiency/deficiency (eg, Addisonian symptoms such as fatigue, muscle weakness, decreased appetite, nausea, vomiting, joint and muscle pain) by study staff during periods of steroid tapering, as appropriate.
- After Week 24, further tapering of glucocorticoids is permitted, however, the taper should not exceed a decrease of 1 mg/day prednisone equivalent per month (eg, 5 mg/day to 4 mg/day over a 1-month time period). Investigators should monitor these participants for signs and symptoms of Addisonian crisis.

Epidural, Intravenous, Intramuscular, Intra-articular, Intrabursal injection, and Intralesional Glucocorticoids

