2. STATISTICAL HYPOTHESES

The primary hypothesis of this study is that guselkumab plus standard-of-care is superior to placebo plus standard-of-care in participants with active LN as measured by the proportion of participants inducing at least a 50% reduction of proteinuria with protocol specified steroid tapering regimen at Week 24.

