5.3.1. Definition of Endpoint(s)

The primary endpoint is the proportion of participants achieving at least 50% decrease in proteinuria from baseline at Week 24. Proteinuria is based on UPCR.

Variable specific data handling rules: Observed data will be used for the analysis.

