5.3.2.1. Primary Estimand (Composite Estimand)

a. **Study intervention:**

- Guselkumab (experimental treatment/intervention) in addition to standard-of-care
- Placebo in addition to standard-of-care

b. **Population:** Participants between 18 and 75 with active LN (defined by meeting the classification criteria for SLE by the 2019 European League Against Rheumatism (EULAR)/ACR, having a Class III or IV predominant kidney biopsy documentation of ISN/RPS proliferative nephritis within the last 6 months prior to or during screening despite receiving one or more standard-of-care treatments.

c. **Variable:** Responder binary variable, defined as a participant achieving at least 50% decrease in proteinuria from baseline at Week 24 who does not:

- discontinue study intervention for any reason excluding COVID-19 related discontinuations or
- meet the Medication Intercurrent Event in Section (e) below

d. **Summary measure (Population-level summary):** Difference in proportion between the study interventions

e. **Intercurrent events and their corresponding strategies:**

Intercurrent Events	Strategy for Addressing Intercurrent Events and Its Description
Discontinuation (DC) of study intervention for any reason excluding COVID-19 related discontinuations	Composite Strategy: A participant with this intercurrent event is considered to not have achieved at least 50% decrease in proteinuria after this event, the occurrence of this intercurrent event being captured in the variable definition.

Medication Intercurrent Event
 
 1. Exceeding baseline glucocorticoid dose 2. Increase above 10 mg/d prednisone equivalent after Week 12, use of new or increased dose of concomitant medication related to LN or other immunosuppressive agents, within 8 weeks prior to the endpoint 3. Initiation of prohibited medications at any time prior to the endpoint 
Note: adjustments in glucocorticoids are permitted up to and including Week 12. Nonsystemic glucocorticoids, NSAIDs, antimalarials and topical agents will not be considered an intercurrent event.
	
Composite Strategy: Same as above

--	---

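### No intercurrent event in the primary estimand covers failure to taper, so a participant held at a constant steroid dose above 10 mg/d can count as a responder

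*SAP*

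**What the plan says.** The hypothesis in SAP 2 is superiority in the proportion "inducing at least a 50% reduction of proteinuria with protocol specified steroid tapering regimen at Week 24"; Protocol 9.1 says the same. Protocol 4.2 gives the reason for the taper: "to minimize confounding treatment effects of glucocorticoids on major efficacy endpoints".

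The endpoint definition in SAP 5.3.1 carries no steroid condition: "The primary endpoint is the proportion of participants achieving at least 50% decrease in proteinuria from baseline at Week 24". Any link to the taper must therefore come from the Medication Intercurrent Event in SAP 5.3.2.1, which has three items:

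1. "Exceeding baseline glucocorticoid dose"
2. "Increase above 10 mg/d prednisone equivalent after Week 12", together with new or increased LN-related or immunosuppressive medication, within 8 weeks before the endpoint
3. "Initiation of prohibited medications at any time prior to the endpoint"

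A note adds that "adjustments in glucocorticoids are permitted up to and including Week 12".

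Protocol 6.5.2 requires adherence to the taper as closely as possible, down to 5 mg/d by Week 12. It also foresees that, for worsening disease in Weeks 2 to 12, "further dose decreases may be suspended, and/or their oral glucocorticoid dose may be temporarily increased". Its treatment-failure (TF) rule after Week 12 is, like the SAP's, worded as an increase above 10 mg/d. Under SAP 5.3, the composite estimand is the only primary-endpoint analysis that will appear in the CSR.

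**The concern.** The items respond to a dose going up. They do not respond to a dose that fails to come down. Take two participants whose UPCR halves by Week 24. One enters at 40 mg/d, has the taper suspended and is still at 40 mg/d at Week 24: none of the three items is met, and this is a responder. The other tapers to 5 mg/d and rises to 12.5 mg/d at Week 20: item 2 is met, and this is a non-responder on far less steroid.

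The variable analysed then differs from the hypothesis, because it mixes responses on the taper with responses off it. Suspension follows worsening disease, so its frequency may differ by arm. More untapered responders on placebo would shrink the difference; more on guselkumab would create one.

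The same item is used for TF (SAP 5.3.2.6, through 5.4.2.1.5), the 50% decrease at Week 52, UPCR <0.5 and UPCR <0.75. CRR is protected by its own limit of 10 mg/d or less (SAP 5.4.2.1.1), and the sustained-reduction endpoint by its dose level (SAP 5.4.2.1.3).

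**Working it through.** **Step 1: apply the rule.** Hold the dose constant from Week 0 to Week 24 at each starting dose in the taper table of Protocol Appendix 7.

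| Constant dose (mg/d) | Item 1: above baseline | Item 2 as an increase | Item 2 as a level above 10 mg/d |
|---|---|---|---|
| 10 | no | no | no |
| 15, 20, 30, 40, 50 | no | no | yes |
| 60 | no | no | yes |

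Item 3 needs a prohibited drug to be started. The list in Protocol 6.5.7 includes multiple administrations of oral steroid averaging 60 mg/d or more, so it may reach the last row. It does not reach 15 to 50 mg/d. A participant on the Appendix 7 schedule is at 10 mg/d or less from Week 8, so the level reading reclassifies nobody who tapers on schedule.

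**Step 2: reproduce the plan's power.** Inputs from SAP 3 and 1.2: placebo response 49%, difference 30 points, total N 60 allocated 1:1, one-sided alpha 0.10. Summing the exact binomial probabilities of every outcome in which a one-sided pooled two-proportion z test rejects, with 30 per arm, gives 89.84% for 49% vs 79%. That is the SAP's own figure. The method also matches the 25-point and 35-point rows (79.61%, 96.08%). It does not match the 20-point row (65.9% against 56.34%), which is not used here.

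**Step 3: bias toward no difference.** The documents give no non-taper rate, so the shares and response rates below are assumptions. Take 49% and 79% as the rates with untapered participants scored as failures. Then:

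observed rate = on-taper rate + (share untapered × response among them)

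With 15% of placebo and 5% of guselkumab participants untapered:

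- 30% of them respond: placebo 0.49 + 0.15 × 0.30 = 0.535; guselkumab 0.79 + 0.05 × 0.30 = 0.805; difference 27 points; power 85.2%.
- 60% of them respond: placebo 0.49 + 0.15 × 0.60 = 0.58; guselkumab 0.79 + 0.05 × 0.60 = 0.82; difference 24 points; power 79.4%.

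With 10% untapered in both arms and 60% responding, each rate rises by 0.10 × 0.60 = 6 points and the difference stays at 30.

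**Step 4: bias toward a false benefit.** Set both arms to 49% on the taper. The test rejects with probability about 12% (above the nominal 10% because outcomes are discrete). If untapered responders add 10 points to guselkumab alone, 49% vs 59% gives about 35%. The normal approximation gives 10% and 30.6%.

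**The case against.** **The protocol does press for the taper.** Besides documenting reasons, it requires adherence as closely as possible, asks that significant deviations be discussed with the medical monitor, and encourages tapering to resume as soon as practical. It does not expressly allow a dose to be held to Week 24, and worsening renal function is a ground to consider discontinuation (Protocol 7.1), which is itself a composite failure. This stands and should keep the number of cases down. None of it makes an untapered participant a non-responder.

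**Item 2 may be meant as a dose level.** If so, the gap closes. But where the SAP wants a level it states one, as in CRR, and SAP 5.4.2.1.3 has both a level condition and a separate rule on increases. At best the item is ambiguous, and the same clarification is needed.

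**It may be deliberate.** SAP 5.3.2 asks about benefit together with protocol-allowed background medication, and temporary suspension is allowed. CRR at Week 24 and sustained steroid reduction stay in the CSR, so non-tapering will be visible beside the primary result. That helps interpretation but does not change who counts as a primary responder, or align that count with SAP 2.

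**Steroid-driven response is not shown.** Inclusion criterion 10 requires UPCR of at least 1.0 on the stable dose intended at randomization, so an untapered participant remains on a dose under which qualifying proteinuria persisted. This stands: the documents support a mismatch with the hypothesis and possible confounding, not a demonstrated steroid effect.

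**Conclusion.** The gap is in the text and does not depend on any assumed rate. As written, a constant dose above 10 mg/d and below about 60 mg/d meets no steroid item, so such a participant is a primary responder if UPCR falls by at least 50% and no other event occurs. That contradicts the stated hypothesis and affects the only primary analysis to be reported. It should be corrected before unblinding.

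The size is illustrative. A power loss of about 5 points (89.8% to 85%) or 10 points (to 79%), and a rise in false success from about 12% to 35%, rest on assumed non-taper shares and response rates, on 30 per arm and on an unadjusted z test rather than the planned logistic repeated-measures model. Enrolment will stop short of 60, so 90% is no longer the operative starting power.

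A reader might infer more than the documents support:

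- That an increase above 10 mg/d is the only steroid event. Item 1 covers a dose above baseline, and item 3 covers prohibited steroid use.
- That every non-taperer is a responder. The UPCR criterion must still be met with no other event.
- That the gap clearly extends to 60 mg/d. The prohibited-therapy list makes that end arguable.
- That the bias has a known direction. It depends on which arm has more untapered responders.

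**What to change.** In SAP 5.3.2.1, define the prednisone part of item 2 as a dose level: an average daily dose above the SAP's existing 10 mg/d limit after Week 12, whether reached by an increase or by not tapering. Use the 7-day average already in SAP 5.4.2.1.3. Keep each estimand's existing time window and strategy, and keep the separate allowance for one short non-SLE/LN course between Weeks 24 and 44 where it appears.

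Make the same change wherever the item is shared, so that one event does not carry two definitions: 5.3.2.1 to 5.3.2.6 (5.3.2.6 supplies the TF definition), 5.4.2.2.1, and 5.4.2.2.3 to 5.4.2.2.7. Protocol 6.5.2 words its TF rule as an increase above 10 mg/d, so the two documents must be reconciled, and the change should be recorded in SAP Appendix 2.

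The cost is SAP wording and programming before unblinding. Steroid dosing is already recorded and is needed for secondary endpoint 2. Response rates may be slightly lower, because some participants now counted as responders become non-responders. The change concerns analysis classification only: no participant's steroid treatment changes and no clinical rule is proposed.

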In the main study and the LTE, treatment for an LN flare, which is defined as an increase in proteinuria and/or serum creatinine concentration, abnormal urine sediment or a reduction in creatinine clearance rate as a result of active disease requiring a change in an immunomodulatory medication for LN beyond that which is outlined in [Table 5](#) and [Table 6](#) will require discontinuation of study medication.

Table 5: Permitted Concomitant Medications for SLE and LN, the Minimum Stabilization Period before Randomization, and the Maximum Allowed Doses at Study Randomization

Permitted Concomitant Medications for SLE	Stabilization Period Prior to Randomization	Maximum Allowable Dose
Antimalarials (chloroquine, hydroxychloroquine, or quinacrine)	Treated for ≥ 12 weeks with stable dosing for ≥ 6 weeks	≤ 250 mg/day chloroquine (≤ 3 mg/kg/day) ≤ 400 mg/day hydroxychloroquine ≤ 100 mg/day quinacrine
Oral glucocorticoids	Treated for ≥ 6 weeks with stable dosing ≥ 2 weeks before randomization. Must not have received epidural, IV, or IM administration of glucocorticoids at a prednisone equivalent dose of > 125 mg/day within 6 weeks prior to randomization.	Equivalent to average daily dose of 1 mg/kg/day or ≤ 60 mg/day of prednisone or its equivalent, whichever is lower
NSAIDs and other analgesics	At least 2 weeks	No more than the usual marketed doses approved in the country where the study is being conducted
Anti-hypertensive medications (ARBs or ACE inhibitors)	At least 2 weeks	No more than the usual marketed doses approved in the country where the study is being conducted.
Non-biologic immunomodulators: MMF MPA	Treated for ≥ 8 weeks at randomization	≤ 3 g/day ≤ 2.2 g/day

Abbreviations: ACE=angiotensin-converting enzyme; ARB=angiotensin II receptor blockers; IM=intramuscular; IV=intravenous; LN=lupus nephritis; MMF=mycophenolate mofetil; MPA=mycophenolic acid; NSAID=non-steroidal anti-inflammatory drug; SC=subcutaneous; SLE=systemic lupus erythematosus.

[Table 6](#) summarizes the protocol requirements and any allowed changes in dosing for study-permitted SLE and LN medications during the double-blind study period.

Table 6: Blinded Study Period - Protocol Requirements for Permitted Concomitant SLE or LN Medications

Permitted Concomitant Medications for SLE ^a	Study Dose at Randomization	Maximum Allowable Dose During Study

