6.5.2. Glucocorticoid Therapy

Participants likely to require multiple courses of systemic glucocorticoids for reasons other than SLE or LN (eg, history of uncontrolled asthma, uncontrolled chronic obstructive pulmonary disease, etc) should be excluded from study participation, including the LTE. However, participants may receive short courses (10 days or less) of oral glucocorticoids for reasons such as prophylactic therapy before surgery (stress-dose glucocorticoids), therapy for certain infections, acute exacerbation of asthma or chronic obstructive pulmonary disease, or other condition (eg, contact dermatitis) not related to increased SLE or LN disease activity. Dosage, duration, and reason for glucocorticoid use in these instances must be documented.

Unnecessary changes in glucocorticoid dose are discouraged, and any dose adjustments are recommended to be made in small amounts. Changes in glucocorticoid dosing other than those described in this section of the protocol are allowed only for medical necessity. The degree and timing of any unspecified glucocorticoid adjustments should be carefully considered as this may have a significant impact on the study results and upon continuation of study intervention.

Oral Glucocorticoids

Participants must be receiving this medication at screening and be on a stable dose equivalent to an average daily dose of 1 mg/kg/day or ≤ 60 mg/day prednisone (or equivalent), whichever is lower for at least 2 weeks prior to the first study intervention dose. Participants are required to be receiving at least 10 mg/day prednisone equivalent at screening and randomization.

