9.4.2. Primary Endpoint(s)

The primary endpoint is the proportion of participants achieving at least a 50% decrease in proteinuria from baseline at Week 24.

Primary endpoint analysis

Analyses of the primary efficacy endpoint ($\geq 50\%$ decrease in proteinuria from baseline at Week 24) will include data from all randomized participants who received at least one administration of study intervention based on their assigned intervention group, regardless of the actual intervention received and have baseline data (Evaluable population).

Treatment Failure Criteria may include: initiation or increased use of a glucocorticoid or other immunosuppressive agents, however these will be further defined in the SAP.

Participants who meet any of the TF criteria defined in the SAP will be assumed a non-responder, ie, did not meet the $\geq 50\%$ decrease in proteinuria criteria at Week 24.

The primary analysis will be based on the composite estimand where participants meeting TF criteria are assumed non-achievers from the point of TF forward, and missing data are assumed as non-achievers as well.

The study will be considered a success if the 1-sided p-value from the difference in proportion of participants with $\geq 50\%$ decrease in proteinuria between the guselkumab and placebo intervention groups from a logistic MMRM longitudinal model is less than a 1-sided alpha of 10%.

See the SAP for further details about the analysis of the primary endpoint, including sensitivity and subgroup analyses.

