5.3.2.6. Supplementary Estimand 5 (Composite)

a. **Study intervention:**

- Guselkumab (experimental treatment/intervention) in addition to standard-of-care
- Placebo in addition to standard-of-care

b. **Population:** Participants between 18 and 75 with active LN (defined by meeting the classification criteria for SLE by the 2019 European League Against Rheumatism (EULAR)/ACR, having a Class III or IV predominant kidney biopsy documentation of

ISN/RPS proliferative nephritis within the last 6 months prior to or during screening despite receiving one or more standard-of-care treatments.

- c. **Variable:** Responder binary variable, defined as a participant achieving at least 50% decrease in proteinuria from baseline at Week 24 who does not:
- discontinue study intervention for any reason excluding COVID-19 related discontinuations or
 - meet the Medication Intercurrent Event in Section (e) below
- d. **Summary measure (Population-level summary):** Difference in proportion between the study interventions
- e. **Intercurrent events and their corresponding strategies:**

Intercurrent Events	Strategy for Addressing Intercurrent Events and Its Description
Discontinuation (DC) of study intervention for any reason excluding COVID-19 related discontinuations	Composite Strategy: A participant with this intercurrent event is considered to not have achieved at least 50% decrease in proteinuria after this event, the occurrence of this intercurrent event being captured in the variable definition.
Medication Intercurrent Event 
 1. Exceeding baseline glucocorticoid dose 2. Increase above 10 mg/d prednisone equivalent after Week 12, use of new or increased dose of concomitant medication related to LN or other immunosuppressive agents 3. Initiation of prohibited medications at any time prior to the endpoint 
Note: adjustments in glucocorticoids are permitted up to and including Week 12. Nonsystemic glucocorticoids, NSAIDs, antimalarials and topical agents will not be considered an intercurrent event.
	Composite Strategy: Same as above

4. **Difference from Primary Estimand:** The first Medication Intercurrent Event, “Increase above 10 mg/d prednisone equivalent, use of new or increased dose of concomitant medication related to LN or other immunosuppressive agents” can occur at any time after Week 12, not just within 8 weeks prior to the endpoint.

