5.4.2.1.5. Time to Treatment Failure (TF)

Time to TF is defined as time to the first occurrence of TF from baseline. TF is defined as the intercurrent events for the Supplementary Composite Estimand 5 of the primary endpoint in Section 5.3.2.6.

5.4.2.2. Estimand(s)**5.4.2.2.1. Proportion of Participants Achieving Complete Renal Response (CRR) at Week 24****Composite Estimand****1. Study intervention:**

- Guselkumab (experimental treatment/intervention) in addition to standard-of-care
- Placebo in addition to standard-of-care

2. Population: Participants between 18 and 75 with active LN (defined by meeting the classification criteria for SLE by the 2019 European League Against Rheumatism (EULAR)/ACR, having a Class III-IV kidney biopsy documentation of ISN/RPS proliferative nephritis within the last 6 months prior to or during screening despite receiving one or more standard-of-care treatments.

3. Variable: Responder binary variable, defined as a participant achieving Complete Renal Response (CRR) at Week 24 who does not:

- discontinue study intervention for any reason excluding COVID-19 related discontinuations or
- meet the Medication Intercurrent Event in Section (5) below

4. Summary measure (Population-level summary): Difference in proportion between the study interventions

5. Intercurrent events and their corresponding strategies:

Intercurrent Events	Strategy for Addressing Intercurrent Events and Its Description
Discontinuation (DC) of study intervention for any reason excluding COVID-19 related discontinuations	Composite Strategy: A participant with this intercurrent event is considered to not have achieved CRR after this event, the occurrence of this intercurrent event being captured in the variable definition.
Medication Intercurrent Event 
 1. Exceeding baseline glucocorticoid dose 2. Increase above 10 mg/d prednisone equivalent after Week 12, use of new or increased dose of concomitant medication related to LN or other immunosuppressive agents, within 8 weeks prior to the endpoint 3. Initiation of prohibited medications at any time prior to the endpoint 
Note: adjustments in glucocorticoids are permitted up to and including Week 12. Nonsystemic glucocorticoids, NSAIDs, antimalarials and topical agents will not be considered an intercurrent event.
	Composite Strategy: Same as above

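### A steroid rise confined to Weeks 12–16 is a treatment failure under the SAP's TF definition but, on the SAP's own note, not an event in its primary Week 24 estimand; the SAP is also inconsistent on what its 8-week limit covers

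*SAP*

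**What the plan says.** **Primary estimand (SAP 5.3.2.1).** A participant is a non-achiever after stopping study intervention (COVID-19 reasons apart) or after a medication event. Item 1 is a glucocorticoid dose above baseline. Item 2 is a prednisone-equivalent rise above 10 mg/d after Week 12, followed in the same list by "use of new or increased dose of concomitant medication related to LN or other immunosuppressive agents, within 8 weeks prior to the endpoint". Item 3 is starting a prohibited medication. The Week 24 CRR and UPCR estimands (5.4.2.2.1, 5.4.2.2.5, 5.4.2.2.6) use the same list.

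**Supplementary Estimand 5 (SAP 5.3.2.6).** Item 2 appears without the 8-week phrase. The note on how it differs from the primary estimand names the rise above 10 mg/d among the events that "can occur at any time after Week 12, not just within 8 weeks prior to the endpoint".

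**Time to TF (SAP 5.4.2.1.5).** "TF is defined as the intercurrent events for the Supplementary Composite Estimand 5 of the primary endpoint".

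**Protocol.** Section 6.5.2: "Increases above 10 mg/day prednisone equivalent after Week 12 will be considered a TF", with no time limit. Section 9.4.2: "Participants who meet any of the TF criteria defined in the SAP will be assumed a non-responder", and in the composite estimand "participants meeting TF criteria are assumed non-achievers from the point of TF forward". Section 9.4.3 treats TF as non-response for the secondary endpoints as well.

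**Reporting.** Under SAP 5.3 the CSR runs only the primary composite estimand, so the Estimand 5 analysis (5.3.4.6) is dropped. SAP 5.4 keeps time to TF. SAP Appendix 2, on changes to protocol-planned analyses, reads N/A.

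**The concern.** The protocol ties the primary endpoint to TF: whoever meets a TF criterion set in the SAP is a non-responder at Week 24. The SAP gives one express TF definition, and it is wider in time than the event list of its own primary estimand. The same participant can then be counted as a treatment failure in the time-to-TF analysis and as a responder in the primary analysis. No departure from the protocol is declared, and the one specified analysis that would show the effect has been removed from the CSR.

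At stake is whether the primary result follows the rule stated in the protocol. If the mismatch is noticed only after unblinding, choosing between the two definitions would be a data-dependent decision.

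**Working it through.** No figure in the plan bears on this point. The check is window arithmetic plus one case run through each rule.

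**1. The uncovered interval.** Inputs: endpoint at Week 24, limit of 8 weeks, TF rule starting after Week 12.
- Start of the window: 24 − 8 = Week 16.
- Gap: 16 − 12 = 4 weeks, out of 24 − 12 = 12 weeks, or 4 × 7 = 28 days.
- If the 8 weeks are counted back from an actual visit at ±7 days (protocol Table 1, footnote b), the visit falls at Week 23 to 25, the window opens at Week 15 to 17, and the gap is 3 to 5 weeks.

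**2. The doses that escape item 1.** Item 1 needs a dose above baseline, so the escaping band runs from above 10 mg/d up to baseline. Baseline must be at least 10 mg/d (protocol inclusion criterion 6.1). The taper columns in protocol Appendix 7 start at 60, 50, 40, 30, 20, 15 and 10 mg. Six of the seven start above 10 mg; in the 10 mg column the band is empty. These are table columns and say nothing about how many participants are in each.

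**3. The clearest case.** Protocol 6.5.2 says "participants may receive short courses (10 days or less) of oral glucocorticoids for reasons such as prophylactic therapy before surgery", and for other reasons unrelated to SLE or LN activity. Take a participant in the 30 mg column, tapered to 5 mg by Week 12, who has one such 10-day course shortly after Week 12, above 10 mg/d but not above 30 mg/d, and stays on study intervention. The course fits in the gap with 28 − 10 = 18 days to spare.

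| Rule | Result |
|---|---|
| Primary item 1: above baseline | Not met |
| Primary item 2, as the 5.3.2.6 note reads it | Not met: over before Week 16 |
| Primary item 3: prohibited drug | Not met: a permitted oral course |
| Stopping study intervention | Not met: treatment continues |
| SAP TF definition (5.4.2.1.5 through 5.3.2.6) | Met |
| Protocol 6.5.2 TF sentence | Met |
| Protocol 9.4.2 | Non-responder from that point |

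So the participant is a TF in the time-to-TF analysis and can be a responder in the primary and Week 24 UPCR analyses. Week 24 CRR is also possible, since its steroid condition (10 mg/d or less) is satisfied once the dose has come down.

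**4. Does the 8-week phrase cover the steroid rise?** Two parts of the SAP answer differently.
- The 5.3.2.6 note says yes: it presents removal of the 8-week limit on the rise above 10 mg/d as a difference from the primary estimand.
- The Week 52 supplementary estimands (5.4.2.2.3.2, 5.4.2.2.4.2) point the other way. They keep item 2 with its 8-week phrase and remove only the exemption for one short non-SLE/LN course in Weeks 24–44. Their notes then treat such a course as non-achievement. With the limit on the steroid rise, the window would open at 52 − 8 = Week 44, and a course in Weeks 24–44 would fall outside item 2. It would fail only if it also exceeded baseline, a condition the notes do not state. They make sense if the steroid rise has no limit.

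Neither note is clean. The 5.3.2.6 note calls item 2 the first medication event, and the note in 5.4.2.2.3.2 speaks of CRR although its endpoint is the proteinuria decrease.

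**The case against.** **The limit may not apply to steroids.** In 5.3.2.1 the 8-week phrase closes a comma list and could attach only to new or increased concomitant medication. The Week 52 notes support that. On this reading the steroid conflict in the primary estimand disappears. This stands as a real ambiguity and is why confidence is moderate. It does not rescue the text, because the 5.3.2.6 note would then be wrong.

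**The protocol leaves TF to the SAP.** Section 9.4.2 does so, and Section 9 presents its content as the original plan, for information. But Section 9 also says that the primary efficacy analysis will be performed, the SAP's express TF definition has no limit, and protocol 6.5.2 lies outside Section 9. Leaving the criteria to the SAP is what produces the conflict.

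**An unlimited definition is natural for a time-to-event endpoint, and 5.3.2.6 shows the difference openly.** Both are fair. They explain why two definitions might exist. Section 5.3.2.6 compares two estimands, though; it does not declare a departure from protocol 9.4.2.

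**The case is narrow.** This stands. It needs a baseline above 10 mg/d, a rise that stays within baseline, a return before Week 16 and continued treatment. A rise made for LN activity may fall under the flare rule in protocol 6.5 (active disease "requiring a change in an immunomodulatory medication for LN beyond that which is outlined in" Tables 5 and 6), which requires stopping study medication and so is already an event. The clean remainder is the permitted short course for other reasons.

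**Stronger readings that do not hold.** A reader might carry the subtraction over to Week 52 and infer that rises in Weeks 12–44 go uncounted there. The Week 52 notes contradict that, so no Week 52 gap is claimed. A reader might also infer that the trial's result hinges on this rule, since fewer than 60 participants will be enrolled. Recoding any one participant could matter in a small trial, but the documents give no probability that this recoding occurs, so it does not add to the severity.

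**Conclusion.** The point holds in limited form and should be fixed; confidence is moderate. On the SAP's own explanatory note, a rise above 10 mg/d but within baseline that is confined to roughly Weeks 12–16 is a TF under SAP 5.4.2.1.5 and protocol 6.5.2, but not an event in the primary Week 24 estimand, contrary to protocol 9.4.2. The interval is 4 of 12 weeks under nominal timing. How many participants are affected, and in which arm, cannot be derived from the documents, so neither the size nor the direction of any effect on the result is claimed.

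The conclusion assumes that the 5.3.2.6 note states the intended scope of the limit. If the Week 52 notes state it instead, the conflict over steroid rises goes away and what remains is an internal contradiction in the SAP. In both cases the wording needs correcting. The SAP also does not say whether item 2 counts the date of an increase or any day above 10 mg/d in the window, so a rise that starts before Week 16 and continues past it is unresolved.

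**What to change.** Before database lock and unblinding:

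- State in item 2 which parts of the list the 8-week phrase covers, and whether it counts the date of the increase or any day above 10 mg/d within the window.
- Make SAP 5.3.2.1, 5.3.2.6, 5.4.2.1.5 and the Week 52 estimand notes agree with each other and with protocol 6.5.2, 9.4.2 and 9.4.3.
- If the 8-week version stays primary for steroid rises, enter the departure from protocol 9.4.2 in Appendix 2 and restore the already specified Estimand 5 analysis (5.3.4.6) to the CSR beside time to TF.

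The cost is SAP wording and, if the limit stays, one Appendix 2 entry and one more table; concomitant therapy is already recorded throughout the study. Response rates in that table may be slightly lower, because Estimand 5 as written also counts permitted short courses above 10 mg/d after Week 12. The primary estimand need not be replaced. No steroid or treatment rule is proposed here; the passages have to be reconciled.
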